| Roles and Responsibilities | Principal Investigator: [name] MD, responsible for study design, overall project oversight, and compliance. Study Coordinator: [name], responsible for daily operation, protocol adherence and patient coordination at Kaizo Health Centers. [name] assisted [name] with initial study design, ongoing recruitment recommendations, pain measure decision-making, study flow creation. [name] PhD (Deceased), responsible for initial power analysis, statistical support for study design, revisions after FDA. [name] PhD, responsible for programming of data collection instruments, ongoing support of data collection tool and dataset, database consolidation; [name] PhD, responsible for statistical analysis of completed dataset. All apart from [name] reviewed the manuscript. |
| Introduction | Low back pain (LBP) affects nearly 40% of adults, contributing to significant reductions in quality of life and productivity. The opioid epidemic, largely driven by prescriptions for pain, has created an urgent need for effective non-pharmacological pain treatments. Existing options such as TENS devices may provide acute relief, but are not available as an opioid substitute. A multimodal approach, combining mechanical stimulation, heat, cold, and acupressure, holds promise for reducing both acute and chronic pain and opioid prescribing. |
| Background and rationale for the study | Between 25 and 50% of patients presenting with acute or exacerbated chronic LBP (a/cLBP) receive prescriptions for opioids. ALBP progresses to chronic in 40% of those with moderate to severe pain (4 out of 10 on a 0 – 10 Numeric Rating Scale). Opioid pain relief is no better than placebo at 6 weeks after presentation, but increases the risk of cLBP and persistent use (5% of opioid naïve). Providing a multimodal low back pain device could reduce opioid prescribing or use compared to TENS; providing any device could reduce opioid prescribing and use compared to contemporaneous prescribing practices. |
| Objectives | Primary Objective, Opioids: To determine whether the use of a multimodal neuromodulatory mechanical stimulation (M-Stim) device (DuoTherm) can reduce opioids 30% compared to TENS in those with moderate to severe back pain. |

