| | Participants will be instructed to use the device for a minimum of 30 minutes a day. Both M-Stim and LG Smart TENS groups will receive a standard pain management regimen typically used for low back pain standardized across all clinicians participating in the study. Participants will keep the devices and be instructed to use them for pain as needed during the duration of the study. |
| Outcomes | Opioid Use Primary Outcome: |
| | Prior use: For patients with prior or ongoing opioid use, a 30% reduction in MME (Milligram Morphine Equivalents) between the first 14 days and the last 14 days of daily diary recordings using the DOSE data collection tool. |
| | Opioid naïve: 30% reduction of those receiving an opioid prescription "prescribed to me for this event" |
| | Secondary outcomes: Use days; total MME and use past 7 days in the opioid naïve; use days by those with more severe pain using the NIH Research Taskforce definitions; and prescribing compared to a contemporaneous national LBP population (25%). |
| | Pain Primary Outcome: |
| | Chronic: 30% lower disability at 6 months using PROMIS Pain Interference for those with ongoing pain >3 months |
| | Acute: 30% lower NRS 0-10 "pain now" from entry to 10 days for those presenting with an episode of pain starting within the past 2 weeks |
| | Secondary Outcomes: Change in disability for those with >=57.7 PROMIS Pain Interference; restoration of function to normal (PI=50); |

| | integrated analysis with | n common | criteria fo | r restoration | on of function | on with | |
|-------------------------|---|---------------|--------------------|---------------------|----------------------|----------------------------|--|
| | multifidus stimulation s | surgery. | | | | | |
| | | | | | | | |
| Participant Timeline | | Initial Visit | Daily x 28 days | Weekly for 3 months | Monthly for 3 months | Monthly 4 - 6 months | |
| | Consent, Enrollment, Randomization | ALBP, CLBP | | | | | |
| | Minimum Dataset, Pain Catastrophizing Sullivan, PROMIS Depression, Physical Function | ALBP, CLBP | | | | | |
| | NRS (at that moment & past 24 hours) | ALBP, CLBP | ALBP, CLBP | ALBP, CLBP | ALBP, CLBP | CLBP | |
| | NRS after 30 minutes | ALBP, CLBP | | | | | |
| | NRS Past week | | | ALBP, CLBP | ALBP, CLBP | CLBP | |
| | NRS Past month | | | | ALBP, CLBP | CLBP | |
| | PROMIS Pain Intensity, Pain Interference | ALBP, CLBP | | ALBP, CLBP | ALBP, CLBP | CLBP | |

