| | Dose, Opioid formulation, number Source (DOSE tool), other analgesics | ALBP, CLBP | ALBP, CLBP | ALBP, CLBP | ALBP, CLBP | CLBP | |
| | Device usage | | ALBP, CLBP | ALBP, CLBP | ALBP, CLBP | CLBP | |
| Sample Size | To estimate the M-Stim | interventi | on effect : | size, a retro | spective st | udy of | |
| | 59 cLBP patients on ch | ronic opioi | ds (100% | prolonged | opioid use) | | |
| | reported a 28% reducti | on in MME | after spin | al stimulat | or | | |
| | implantation,[40] reducing MME 26.2(SD32.8) compared to 5.8(SD34.2) | | | | | | |
| | for those with conventional treatment (effect size 0.60. A priori, we would | | | | | | |
| | be able to detect an effect size of 1 (meaning a difference of 1 standard | | | | | | |
| | deviation) with 94% power and alpha of .03 using a Wilcoxon Mann | | | | | | |
| | Whitney test with 30 in each group. With this effect size for a two-sided | | | | | | |
| | significance of 0.05, 17 participants per group would detect a 30% | | | | | | |
| | prescribing reduction, while 50 participants on chronic opioids per | | | | | | |
| | treatment group would provide 85.4% power to detect a 30% reduction in | | | | | | |
| | MME. Given the 20% in a previous study by Jamieson et al, we increased | | | | | | |
| | the cLBP sample to 50 | - | | Jannoson | icat, we iiio | ioasea | |
| | | | | | | | |

| | We planned to recruit 60 aLBP participants who had never taken opioids for their back pain, and 100 cLBP without a new prescription but with or without chronic opioid for cLBP. |
|----------------------------|--|
| Recruitment | Patients were recruited from Kaizo Health Centers in Landover and Fairfax, through direct referrals, flyers, and digital content like social posts and emails targeting local populations. Flyers were also distributed at three local pain clinics. |
| Randomization | After eligibility screening and informed consent, a 4-digit participant ID and the intervention allocation were randomly assigned by the survey software to either the DuoTherm or LG Smart TENS group within acute and chronic arms. A copy of the informed consent was emailed to the participant. |

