Participants recorded when they used their device, duration of use, and any additional pain relief modalities (exercise, stretching, bath, hot tub, therapy, massage). Patients were asked to record any thermal use or therapy cycle or channel as appropriate to their device.

Participants verbally endorsing pain for less than three months (acute) were entered into a 3 month follow-up program, or 6 months (chronic) for those for whom back pain had been an ongoing problem for more than 3 months.

Statistical Methods

Statistical analysis was performed with masked intervention allocation by a statistician new to the project to determine differences in primary and secondary outcomes.

An intention-to-treat analysis included all participants meeting inclusion criteria. Summary statistics (means, standard deviations, proportions) were calculated using T-tests and Chi-squared tests. Opioid prescribing differences were calculated with raw percent of change and relative risks. Diary entries and item-level data were analyzed for missing data to assess the need for imputation. Relative risks were calculated for MME and opioid use days between intervention groups, with paired T-tests used to compare first two and last two weeks of MME in those who used opioids during the study. A linear regression assessed BMI's interaction with opioid use, calculating marginal effects with standard errors via the Delta Method. Data analysis was performed using STATANow/SE 18.5.

For pain outcomes, in addition to the above methods, missing 10 day NRS-1 data will be imputed using forward fill and KNN. A neural network will be created to determine factors contributing to 13 week Pain Interference, with iterative modeling to reduce mean absolute error. Graphs with r-squared for predictors will be generated.

| Data Monitoring | Data collection was conducted through an app that tracked daily pain, opioid use and device usage. Monitoring included weekly enrollment review by the protocol statistician to assess comprehension of the data collection tool. Adverse events were reported as per protocol. | |
|------------------------|---|--|

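### Prior-user opioid primary: the only analysis of the two 14-day windows is a paired T-test with no M-Stim versus TENS contrast, in a group defined by use after randomisation; the between-group relative risk named for MME is undefined

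*Combined protocol and SAP*

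**What the plan says.** **Objective.** The primary opioid objective in Objectives is whether the device "can reduce opioids 30% compared to TENS in those with moderate to severe back pain". This is a comparison between arms.

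**Endpoint and population.** Outcomes sets this endpoint "For patients with prior or ongoing opioid use" and defines it as "a 30% reduction in MME (Milligram Morphine Equivalents) between the first 14 days and the last 14 days of daily diary recordings".

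**Sample size.** The planning effect comes from a retrospective spinal-stimulator study, "reducing MME 26.2(SD32.8) compared to 5.8(SD34.2" for conventional treatment. From this the plan states that 50 participants on chronic opioids per "treatment group would provide 85.4% power to detect a 30% reduction in" MME.

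**Analysis.** Statistical Methods states a general aim of finding differences in the primary and secondary outcomes. It names T-tests and Chi-squared tests for summary statistics. One sentence then says that relative risks for MME and opioid use days were calculated between the intervention groups, "with paired T-tests used to compare first two and last two weeks of MME in those who used opioids during the study". The Wilcoxon Mann-Whitney test appears only under Sample Size.

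**Windows.** Protocol Amendments explains the two fortnights: prescribing records were not available, and a reduction in opioid use was itself a desired outcome.

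**The concern.** There are two faults in the current text.

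1. **No arm contrast.** A paired test asks whether MME changed within participants. Whether it is run pooled or separately by arm, it does not ask whether the change differed between M-Stim and TENS. Natural course or regression to the mean can lower MME in both arms and make it significant. With no between-arm analysis fixed for this endpoint, such a result could be taken as support for an objective that it does not test.

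2. **Wrong population.** Outcomes defines the group by prior or ongoing use. The paired test is restricted by use during the study, which is known only after randomisation and is what the device is meant to change. A prior user who reports no use drops out, although that could be the best possible response. An opioid-naive participant who starts an opioid comes in. The restriction also sits badly with the intention-to-treat statement in the same section.

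**Working it through.** **1. The plan's own power figure.** Inputs are from Sample Size.

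- Pooled SD = sqrt((32.8² + 34.2²)/2) = 33.51.
- d = (26.2 − 5.8)/33.51 = 20.4/33.51 = 0.609.
- Two-sample T-test (noncentral t), 50 per arm, two-sided 0.05: power 85.4%, an exact match.

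The trial was therefore sized for a between-arm comparison.

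**2. What the paired test does when the devices do not differ.** Assume that both arms decline by 5.8/34.2 = 0.17 SD. This is the conventional-treatment figure in Sample Size, assumed to carry over to diary fortnights. The three sizes are the planned 50 prior users per arm; 40 per arm, if half of the planned 160 are prior users; and 25 per arm, if half of the 100 chronic participants are. The half comes from Protocol Amendments, which reports that about half of each stratum had no prior opioids for back pain.

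| Prior users per arm | Paired test significant, one arm | Paired test significant, arms pooled | M-Stim significant, TENS not | Two-sample test on the change |
|---|---|---|---|---|
| 25 | 13% | 22% (n = 50) | 11% | 5% |
| 40 | 18% | 32% (n = 80) | 15% | 5% |
| 50 | 22% | 39% (n = 100) | 17% | 5% |

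The fourth column is p(1 − p), where p is the unrounded one-arm value: 0.129 × 0.871 = 0.112, 0.182 × 0.818 = 0.149 and 0.217 × 0.783 = 0.170. With an assumed decline of 0.3 SD, the one-arm figures rise to 30%, 46% and 55%.

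**3. How far the population could move.** Half of 160 gives about 80 prior users and 80 others.

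- If 10% to 50% of prior users report no use (assumed), 8 to 40 leave.
- If 5% (assumed) to 25% of the others start an opioid, 4 to 20 enter. The 25% is borrowed from the secondary outcome "prescribing compared to a contemporaneous national LBP population (25"%).
- The opioid-naive share of those analysed then runs from 4/(72 + 4) = 5% to 20/(40 + 20) = 33%.

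This shows what the wording allows. It does not estimate what happened.

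**4. Power of a between-arm test of the change.** With d = 0.609, it is 85%, 77% and 56% at 50, 40 and 25 per arm. Keeping prior users who report no use dilutes the effect. With an assumed 25% at zero change in both arms, a T-test has about 71%, 61% and 42%; with 50% at zero, about 51%, 42% and 28%.

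**5. A limit of the windows themselves.** Both fortnights follow randomisation. A proportional cut that is present and constant from day 1 lowers both, so it largely cancels from their difference. The simulation used a lognormal model: median 20, between-person log SD 1, within-person log SD 0.3 to 0.7, and a sustained 30% cut in one arm. All of these are assumed. The between-arm test of the change has about 3% to 5% power, roughly its significance level. A log-scale comparison of days 15–28 has 17–22% (25 per arm) to 30–39% (50 per arm), and of all 28 days 19–23% to 35–40%.

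**The case against.** **A between-arm MME statistic is named, in the very sentence that contains the paired test.** The 30% in Outcomes could serve as a responder cut-off for that relative risk, and the section opens with an aim of finding differences. A reader might infer from the paired test that no between-arm analysis was planned or run. The documents do not support that. What stands is narrower. MME is continuous, and the relative risk has no event, window or population. The responder reading has to be supplied by the reader, so the analysis of this endpoint is not specified.

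**The 13% to 39% figures are not false-positive rates for M-Stim versus TENS.** A reader might infer that they are. They are correct detections of a decline that both arms share, and the plan never calls the paired test a between-arm test. They mislead only if read as a device effect. For by-arm reporting, the misleading pattern is M-Stim significant and TENS not, at 11% to 17%.

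**Power should not be compared by putting 0.609 into a paired formula.** A reader might do so and get a much higher figure, but that uses a between-arm effect size as a within-person one. The exact match at 85.4% is evidence enough.

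**The sizes rest on assumptions.** This is fair: the 0.17 SD comes from another setting, and the shares who stop or start are not in the documents. The two faults do not depend on these numbers. The population conflict rests on Outcomes against Statistical Methods, not on the wording of the amendment history.

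**Conclusion.** The point holds and needs correcting before any result is presented as a test of the opioid objective in prior users. The text as written gives this primary outcome a test of a different question, in a population other than the one it names, and leaves the between-arm analysis undefined. That follows from the wording alone, and the exact reproduction of 85.4% confirms that a between-arm comparison was intended.

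The percentages illustrate the risk of misreading, under an assumed equal decline in both arms and normally distributed changes. They do not show that any reported result is wrong.

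The on-treatment windows are a separate limitation, for which the plan gives its reasons. It is not a fault of the paired test, and it would remain after the correction.

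**What to change.** Change Statistical Methods as follows, and keep the stated endpoint.

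- **Population:** all randomised participants with prior or ongoing opioid use at enrolment, whether or not they later report use.
- **Primary analysis:** the between-arm difference in MME change from the first to the last 14 diary days, by linear regression on arm and randomisation stratum, with a 95% confidence interval. The stratum belongs in the model because allocation was to the "DuoTherm or LG Smart TENS group within acute and chronic arms". Use the Wilcoxon Mann-Whitney test as a sensitivity analysis.
- **Paired test:** label it descriptive, and say whether it is pooled or by arm.
- **MME relative risk:** drop it, or define it as the relative risk of achieving at least a 30% reduction. The second option needs a rule for participants with zero MME in the first fortnight, for whom a percentage reduction is undefined.
- **Windows:** report between-arm MME over days 15–28 or over all 28 days as a sensitivity analysis, not as a replacement primary.

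**Cost.** The work is some wording and a few lines of code; the schedule already records opioid use at the initial visit. Statistical Methods is written in the past tense, so if the analysis is done, the between-arm result must be labelled as added later.

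The statistical cost should be stated openly. Power falls from 85% to 77% or 56% if there are only 40 or 25 prior users per arm, and further if prior users with zero change are kept. With 25% at zero, the Mann-Whitney test is roughly 3 to 5 points below the T-test. Because both fortnights are on treatment, a null result on the change score cannot rule out an effect that was present and constant from the start, and the report should say so.

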| Blinding (masking) | Participants were blinded to which device powered the study hypothesis, and blinded to their assigned intervention until after documenting initial NRS pain intensity. Success of blinding the study device (M-Stim) versus the active control (TENS) was tested at months 3-6 with prompts, "select which group you think you were in (control or treatment)" and "How confident are you (0 = Least Confident 100 = Most Confident)." The protocol statistician and study coordinator knew the intervention assignments during enrollment but did not conduct statistical analysis. The PI and treating chiropractor were blinded to allocation during enrollment, with the PI accessing data only after study completion. The analyzing statistician was blinded to device assignment until completion of data cleaning and initial analysis. |
| Data Collection Methods | Site coordinators entered identification and contact information after informed consent on a tablet, then recorded weight, height, and duration to confirm acute or chronic follow-up duration, then participants took the tablet to record pain intensity on a 0-10 NRS now and past 24 hours. While using the device for 30 minutes, participants completed 7-day pain intensity NRS, NIH Back Pain Research Minimum Dataset, including PROMIS measures of Physical Function, Pain Interference, Depression, and Catastrophizing via the Sullivan Catastrophizing scale, Injury Mechanism, prior treatments, exercise and athletic status. |
| | Participants were prompted to record analgesic use, pain, and device use daily for a month on the web-based platform, then weekly, with the monthly surveys adding Pain Interference. All surveys asked about |

analgesic use. Due to the anticipated heterogeneity of opioid formulations, a skip-logic data collection instrument algorithm was created with robust options for Dose per pill (34), Opioid formulations, e.g. hydrocodone, hydromorphone etc. (15) and the Source (DOSE tool, Supplement 2). Sources included "prescribed to me for this event", "prescribed to me for another event", "given to me by a family member", "given to me by a friend", "given to me by an acquaintance or stranger", or "purchased from someone without a prescription". These were converted to a total milligram morphine equivalent (MME) for analysis.

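### Forward fill and KNN for missing day-10 NRS can shrink or create an arm difference in the acute pain co-primary; the observed daily scores should be modelled instead

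*Combined protocol and SAP*

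**What the plan says.** The Outcomes section sets two pain primaries. The acute one is a 30% lower pain-now NRS "from entry to 10 days for those presenting with an episode of pain starting within the past 2 weeks". The chronic one is "30% lower disability at 6 months using PROMIS Pain Interference".

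The Statistical Methods section gives the analysis. Summary statistics "were calculated using T-tests and Chi-squared tests". The pain paragraph opens "For pain outcomes, in addition to the above methods" and then adds that "missing 10 day NRS-1 data will be imputed using forward fill and KNN". It also adds a neural network for predictors of 13-week Pain Interference and r-squared graphs. The only regression named concerns BMI and opioid use. Diary and item-level data are to be examined for missingness to judge whether imputation is needed. The section does not state:

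- the order in which forward fill and KNN apply, the number of neighbours, or the predictors;
- a baseline-adjusted or longitudinal comparison of the arms;
- a missing-data sensitivity analysis.

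The data for a better analysis are collected. The Participant Timeline schedules "NRS (at that moment & past 24 hours") at entry and daily for 28 days. It schedules "PROMIS Pain Intensity, Pain Interference" at entry and repeatedly afterwards. Under Blinding, participants do not know their device "until after documenting initial NRS pain intensity", so entry NRS is a true pre-device baseline.

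**The concern.** Participants enter with an NRS of at least 4, and the outcome is a fall in pain. An earlier score carried to day 10 is therefore expected to overstate day-10 pain. If the share who stop, the timing of stopping, or the kind of participant who stops differs by arm, the overstatement does not cancel. If these are the same in both arms, a true effect is diluted.

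Unequal stopping is plausible: the devices are visibly different, assignment is known after the first NRS, and the diary is completed unsupervised. The bias can run either way, because heavier loss from TENS flatters M-Stim and heavier loss from M-Stim does the reverse.

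The acute group is also small. Sixty were planned, but the Protocol Amendments section reports that 16 of 60 in the acute stratum gave a duration over three months. If that rules out an episode begun within 2 weeks, at most 60 − 16 = 44 remain from that stratum, about 22 per arm. There may be fewer, because the stratum admits pain of up to 3 months and the endpoint only 2 weeks.

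**Working it through.** **Plan's own figure.** There is none for either pain co-primary. The 94% power under Sample Size (1 SD, 30 per group, alpha 0.03, Wilcoxon Mann Whitney) follows an opioid-dose estimate. It reproduces (93.4% by simulation), but nothing below depends on it.

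**Assumptions, none from the documents.** A linear fall of 3 points over 10 days (0.3 per day) in both arms; SD 2; correlation between entry and day 10 of 0.42. Those who stop do so permanently, with the last recorded day spread evenly over days 0-9 (mean 4.5), so the mean carry is 10 − 4.5 = 5.5 days. The analysis is a T-test on change.

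**1. No true difference, 10% versus 30% stopping.**
- Forward fill: bias = difference in missing share × daily fall × mean carry = 0.2 × 0.3 × 5.5 = 0.33 points.
- Forward fill, then KNN for the tenth of stoppers with no diary entry after entry: 0.2 × 0.3 × 4.5 = 0.27.
- For a 2-point fall: 0.2 × 0.2 × 5.5 = 0.22, and 0.2 × 0.2 × 4.5 = 0.18.
- SD of change = 2 × √(2 × (1 − 0.42)) = 2.15. Standard error at 30 per arm = 2.15 × √(2/30) = 0.556. A bias of 0.33 is then 0.59 standard errors, which gives a two-sided type I error of 9.1%; 0.27 gives 7.7%.
- Simulation: 8.2-9.3% for forward fill and 7.6-8.4% for the combined rule. At 22 per arm: about 8% and 7.4%.

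**2. Skipped days instead of stopping.** If each day is skipped independently with probability p, the mean carry is about p/(1 − p): 0.111 at 10% and 0.429 at 30%. Bias = 0.3 × (0.429 − 0.111) = 0.095, about 0.1 points. The normal approximation gives a type I error of 5.3%; simulations gave 5.4-6.0%. If only day 10 is missed: 0.2 × 0.3 × 1 = 0.06.

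**3. Equal 20% stopping.** A true 0.90 becomes 0.90 × (1 − 0.2 × 0.55) = 0.80 under forward fill, or 0.90 × (1 − 0.2 × 0.45) = 0.82 under the combined rule. Type I error stays at about 5-6%. Power for a true 0.90 is 27-29% with the plan's rule and T-test, against 37-38% for complete-case ANCOVA.

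**4. Does baseline adjustment rescue the filled data?** No. At 10% versus 30% stopping, ANCOVA on the filled data has a type I error of 9.0-9.8%. Complete-case ANCOVA on unfilled data has 4.7-5.0%.

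**5. Selective stopping.** Suppose 20% stop in each arm, but those who stop have higher pain on TENS and lower pain on M-Stim. At 30 per arm, forward fill gives a false 0.33 (type I error 9.7%), the combined rule 0.27 (8.9%), and complete-case ANCOVA errs the other way, −0.25 (7.8%). At 22 per arm the mixed model proposed under the fix gives −0.01 (6.0%). This is why complete-case ANCOVA serves as a check and not as the primary analysis.

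**6. Chronic co-primary, precision only.** With 50 per arm, full follow-up, 80% power and two-sided 5%, the detectable difference in SD units is:

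| Correlation of baseline with 6 months | Change score | 6-month score | ANCOVA |
|---|---|---|---|
| 0.3 | 0.67 | 0.57 | 0.54 |
| 0.5 | 0.57 | 0.57 | 0.49 |
| 0.6 | 0.51 | 0.57 | 0.45 |

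**The case against.** **The headline pattern is severe.** A bias of 0.3 points needs permanent stopping that is three times as common in one arm, and a 3-point fall. With daily prompts for a month, skipped entries are at least as plausible, and they give about 0.1 points. This stands, and the size must be given as a range.

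**The plan does review missingness.** It does, but the review only decides whether imputation is needed. It does not test how the result depends on the filling rule.

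**An unadjusted randomised comparison is valid.** It is. A reader might infer that omitting baseline adjustment biases the pain results, or that the filling rule also touches the chronic outcome. Neither follows: lack of adjustment costs precision only, and the rule is stated for day-10 NRS alone.

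**KNN and understated uncertainty.** A reader might infer that single imputation makes the standard error too small. In simulation this appeared only when within-arm KNN filled every gap (type I error about 9% at 20% missing). The plan also uses forward fill, and with forward fill first and equal missingness the error was 4.9-6.2%.

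**A lighter remedy would do.** Adjusting for baseline while keeping the filled data recovers some power but leaves the bias (step 4).

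**The support for the mixed model is partly circular.** The simulated data had the same covariance form as the model, and only a growing SD was varied. Its type I error was 5.7-6.1%, and simpler variance forms reached 9-10% when the SD grew. It was not tested below 22 per arm. This stands, and it is why a simple fallback is needed.

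**Conclusion.** The concern holds for the acute co-primary. The plan states a filling rule that is biased whenever pain is falling, although it collects data that make the rule unnecessary. The effect runs from little (about 0.1 points and roughly 5% type I error with skipped days) to moderate (about 0.3 points and 8-9% with 10% versus 30% permanent stopping). With equal 20% stopping, about a tenth of a true effect is lost. All of these figures rest on an assumed fall, SD, correlation and stopping pattern.

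A reader might infer that the acute result is biased, or that it favours M-Stim. The documents do not support this: they report no missingness by arm, and the direction depends on which arm loses more. The chronic part is a missed gain in precision and not an error. The change should be made; confidence is medium because the amount of missing data is unknown.

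**What to change.** **Acute co-primary.** Drop forward fill and KNN from the primary analysis.

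- Fit a likelihood-based mixed model to the observed daily pain-now NRS, days 0-10, in those whose episode began within 2 weeks. Enter the pre-device NRS as day 0 with arm means constrained equal, and include day and arm-by-day effects.
- Use a parsimonious covariance with day-specific variances, for example a random intercept plus AR(1): 13 parameters against 66 for an unstructured matrix. Use small-sample degrees of freedom.
- Report the day-10 contrast in points and also against the plan's 30% criterion.
- Give complete-case ANCOVA adjusted for entry NRS as a check, and as the fallback if the model does not converge.
- Add a delta-adjusted multiple-imputation analysis that shifts imputed day-10 values in each arm separately, for example by 0 to 2 points in steps of 0.5, so that a positive and a null result are both tested. Each point moves the contrast by that arm's missing share (0.2 at 20% missing).

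**Precision, separately.** Analyse 6-month Pain Interference by ANCOVA on baseline Pain Interference. Note that the baseline is completed during the first device session, a limit that a change score shares. Include the acute/chronic randomisation stratum in any pooled analysis.

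**Cost.** SAP wording and somewhat more analysis work, with no new data. The model assumes that stopping depends only on recorded pain, hence the delta analysis, and its type I error ran slightly above 5% in simulation. If the pain analysis has already been run, report the replacement beside it and label it post hoc.
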